#### 8 Statistical Methods

#### 8.1 General Reporting Conventions

Study data will be provided in listings and sorted by subject number, study period, and assessment time. The study results will be displayed using descriptive summary tables and inferential analyses completed as described below. Summaries will be displayed by group for all tables and, optionally, for all subjects for baseline tables. For measurements that have multiple intermediate visits, results for observed data will be summarized for each time.

Standard numeric descriptive statistics include number of subjects or records observed (N), mean, standard deviation (std), median, minimum (min), and maximum (max) values. Standard categorical descriptive statistics include the count and percentages of subjects with a level of the variable summarized. Hypothesis tests will assess the null hypothesis that there is no difference in the treatment arms. Two-sided p-values of less than or equal to 0.05 will be considered statistically significant.

All summaries, statistical analyses, and individual subject data listings described below will be completed using Version 9.4 or later of the SAS Statistical Analysis System (SAS Institute, Inc. Cary, NC).

Subjects who are randomized but not treated and those who are treated but have no post-treatment follow-up assessments or data will be listed, but not analyzed. For all listings with dates, the relative study day will be presented, and a minus sign will denote study day is prior to first dose (day 1) while a plus sign will denote number of study days after last dose. Days occurring during treatment period will use neither a plus nor a minus sign.

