9.2. Analysis Populations

Within each population, analyses will be performed comparing subjects and by-treatment assignment (SP-624 vs placebo).

- All Subjects Population – all subjects who sign informed consent and are assigned a unique subject identification number. This population will be used to summarize disposition.
- Modified Intent-to-Treat (mITT) Population – all subjects who are randomized to receive treatment, receive at least one dose of study drug, and have a Baseline and at least one post-dose efficacy assessment. This population will be the primary population used to summarize demographics, baseline characteristics, medical history, treatment history, and all efficacy outcomes. Subjects will be analyzed according to randomized treatment group.
- Per Protocol (PP) Population – All subjects in the mITT population who received assigned study drug as randomized, completed the Week 4 assessments without any major protocol violations, and have 75-125% compliance. The PP population will be used as an additional population for summaries of efficacy outcomes.
- Safety Population — all subjects in the mITT population who receive at least one dose of study drug. Safety subjects will be summarized according to the treatment they actually received, in case they received a different treatment than assigned at randomization. This population will be used to summarize all safety assessments.
- PK Population — all subjects who receive active study drug and have evaluable PK data based on actual treatment received, protocol compliance, adequate numbers of samples, and successful sample assays.

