#### 2.2 Changes to Planned Analyses

The protocol definition of the safety population is all subjects in the mITT population who receive at least one dose of study drug. This population definition has been corrected in section 7 below to all subjects that were randomized to treatment and received at least one dose of study drug. The updated safety population definition will be used for all safety analyses.

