#### 7 Study Populations

The following populations will be considered for this study:

- All Subjects Population all subjects who sign informed consent and are assigned a unique subject identification number. This population will be used to summarize disposition.
- Modified Intent-to-Treat (mITT) Population all subjects who are randomized to receive
  treatment, receive at least one dose of study drug, and have a Baseline and at least one post-dose
  efficacy assessment. This population will be the primary population used to summarize
  demographics, baseline characteristics, medical history, treatment history, and all efficacy
  outcomes. Subjects will be analyzed according to randomized treatment group.
- Safety Population all subjects randomized to treatment and who receive at least one dose of study drug. Safety subjects will be summarized according to the actual treatment they received. This population will be used to summarize all safety assessments.
- PK Population— all subjects who receive active study drug and have evaluable PK data based on actual treatment received, protocol compliance, adequate numbers of samples, and successful sample assays.

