#### 8.3.7.1 Safety Analyses

All summaries of safety and tolerability will be performed on the safety population.

Laboratory parameters, vital sign data, and ECG results will be summarized by treatment group and presented in tabular and graphic formats where appropriate. Appropriate change from Baseline calculations for the mean change from baseline within each treatment group where appropriate will be used for laboratory parameters, vital sign values, ECG results, and C-SSRS results, but no formal statistical tests are planned.

Form STAT401.V3 Page 15 of 23

Client/Project	Arrivo/Sirtsei 201
Version and Date	V01 August 26, 2022

Shift tables will also be provided for laboratory parameters.

Unscheduled and Repeat safety assessments will be listed but will not be summarized in the tabular summaries. Local laboratory results will be listed but will not be summarized in the tabular summaries.

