#### 8.3.7.2 Adverse Events

An AE is any untoward medical occurrence in a clinical study subject, whether or not the event is considered causally related to the study drug. An AE can be a new occurrence or an existing process that increases significantly in intensity or frequency.

All Aes must be recorded in the appropriate section of the CRF.

Adverse event monitoring for each subject begins upon Screening and continues until study completion. Abnormalities present at Screening are considered AEs only if they reoccur after resolution or worsen in intensity or frequency during the study. The events recorded with a start date and time on or after the date and time of the first dose of study drug will be considered Treatment Emergent Aes (TEAEs). Each AE is to be classified as serious or non-serious, and categorized with respect to relationship to study drug, and intensity.

Summaries of the number and percentage of subjects in the safety population with at least one treatment-emergent AE (TEAE), classified according to preferred term and/or body system using the MedDRA dictionary, will be provided overall and by treatment group for:

- Overall summary
- All TEAEs
- TEAEs by relationship (not related, possibly related, probably related)
- TEAEs by severity (mild, moderate, severe)
- SAEs
- TEAEs leading to withdrawal from the study
- TEAEs leading to study drug dose reduction
- TEAEs leading to study drug dose taken with food
- Analyses of Aes with time of onset beginning 24 hours after the final dose through up to 28 days after the final dose.

In addition, a summary will be provided of the number and percentage of subjects in the safety population with at least one pre-treatment AE (i.e., Aes with date and time of onset prior to the first dose of study drug).

Listings of events leading to discontinuation or death will be provided.

No formal statistical tests are planned for AE data.

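### SAP 8.1 keeps an inherited exclusion of treated subjects without post-treatment data, which contradicts the corrected Safety Population in SAP 2.2 and 7

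*SAP*

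**What the plan says.** Protocol 9.2 defined the Safety Population as "all subjects in the mITT population who receive at least one dose of study drug". Because mITT membership requires a Baseline and at least one post-dose efficacy assessment, a dosed subject who was never rated again fell out of the safety tables.

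SAP 2.2, which lists changes to the planned analyses, records this as the one change. By its account, the wording was "corrected in section 7 below to all subjects that were randomized to treatment and received at least one dose of study drug". It also makes the scope explicit: "The updated safety population definition will be used for all safety analyses". SAP 7 repeats the new definition: "all subjects randomized to treatment and who receive at least one dose of study drug". SAP 8.3.7.1 follows ("All summaries of safety and tolerability will be performed on the safety population"), and SAP 8.3.7.2 builds the AE tables on the same group ("Summaries of the number and percentage of subjects in the safety population with at least one treatment-emergent AE"). None of these places asks for any data after dosing.

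SAP 8.1 (General Reporting Conventions) then carries a sentence on two groups. One is subjects who were randomised and never dosed. The other is "those who are treated but have no post-treatment follow-up assessments or data will be listed, but not analyzed". Protocol 9.3.1 has the same wording. The sentence is not restricted to efficacy, and SAP 2.2 does not mention it.

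**The concern.** The SAP corrected the population definition but kept a companion sentence that sets a data condition of its own. Sections 2.2 and 7 say who belongs to the Safety Population; Section 8.1 says who is analysed. A programmer could apply both in turn, and the SAP does not say which prevails.

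At stake are the denominators of every table that SAP 10.1 assigns to the Safety Population. These include the AE summaries, treatment administration and compliance, and protocol deviations. If 8.1 is followed, those tables no longer describe all randomised and dosed subjects, which is what the sponsor set out to achieve in 2.2.

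The reach of the sentence is also unclear. Section 8.1 does not define *post-treatment*. Protocol 6.8 and 9.3.8 use the word for medications started after the last dose, while the mITT definition uses *post-dose* for data after dosing begins.

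**Working it through.** The plan gives no figure on this point to reproduce, so the check is a comparison of rules followed by simple denominator arithmetic.

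**1. The rules side by side**

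| Subject (randomised and dosed) | Protocol 9.2 (superseded) | SAP 2.2 and 7 | SAP 8.1, narrow: no data of any kind after dosing starts | SAP 8.1, wide: no data after the last dose |
|---|---|---|---|---|
| A. AE recorded, never rated for efficacy again | out | in | in | in only if something is recorded after the last dose |
| B. Nothing recorded after dosing starts | out | in | **out** | **out** |
| C. On-treatment visits, then lost with nothing after the last dose | in | in | in | **out** |

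Row B is a contradiction on either reading. Row A shows that the narrow rule is weaker than the old mITT condition. Row C is affected only on the wide reading.

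**2. Size on the narrow reading**

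Inputs: 150 per arm (SAP 5). Assumed: 30 subjects per arm with an AE (30/150 = 20.0%), and a fraction f of dosed subjects with no later data, taken as 1%, 3% and 5%. The documents give neither the AE count nor f.

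Excluded subjects have no recorded event, so the numerator stays at 30:

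reported rate = 30 / [150 × (1 − f)]

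- f = 1%: 30/148.5 = 20.2%
- f = 3%: 30/145.5 = 20.6%
- f = 5%: 30/142.5 = 21.1%

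The distortion is upward and at most about one percentage point. In relative terms the factor is 1/(1 − f), from 1/0.99 = 1.01 to 1/0.95 = 1.05.

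**3. Direction on the wide reading**

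Let d be the fraction removed, with AE rate p_e, and let p_r be the rate in those retained. The table shows p_r; the full Safety Population rate is (1 − d)·p_r + d·p_e. The table understates the rate whenever p_e exceeds p_r, which is plausible if subjects leave because of poor tolerability. The documents give no value for d, p_e or p_r, so no size is claimed.

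**The case against.** The strongest reply is that the specific rule prevails. SAP 2.2 says expressly that the corrected definition governs all safety analyses, three later sections repeat it without exception, and the 8.1 sentence is an inherited general line. That is the sensible reading and probably what the sponsor intends. But the SAP does not state it, and the 8.1 sentence is itself an unqualified instruction.

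The reply is stronger against three inferences that a reader might draw.

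- *That 8.1 reverses the correction in 2.2.* It does not. The old condition required a post-dose efficacy assessment. The main group that 2.2 restores, dosed subjects with safety data but no later efficacy rating, stays in on the narrow reading.
- *That 8.1 removes early leavers and so lowers AE rates.* On the narrow reading, an early leaver with an AE record or a discontinuation visit has data and is kept, and percentages rise. Lower rates need the wide reading, which fits the rest of the plan poorly. It would take subjects with on-treatment ratings out of efficacy, against the mITT definition, and would undercut the plots by dropout week in SAP 8.3.5.5. SAP 8.1.2 assigns Day 1-3 safety assessments to Week 1, and Protocol 5.4 asks for safety follow-up of early leavers where possible. Both show that their data are meant to be tabulated.
- *That the 20-30% dropout in SAP 8.3.5.5 (60-90 of 300) measures the loss.* That figure is a typical dropout rate in depression trials. It is not a rate of subjects with no data after the last dose, and Protocol 5.4 works against treating the two as equal.

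What remains is the contradiction for subjects with no later data, and an undefined term that leaves the wide reading open.

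**Conclusion.** The passage is wrong as written: an internal contradiction with a small expected effect. For a dosed subject with no later data, SAP 8.1 gives the opposite instruction to SAP 2.2, 7, 8.3.7.1 and 8.3.7.2. On the narrow reading the result is denominators that are slightly too small in the AE, exposure and protocol-deviation tables, with a 20.0% AE rate shown as 20.2-21.1%. That range rests on the assumed 1-5% of subjects affected and 30 AE subjects per arm.

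Understated AE and AE-withdrawal rates are possible only on the less likely wide reading, and the documents give no basis for a size. Neither the sample size nor the primary efficacy analysis is affected on the narrow reading, because subjects with no data after dosing are already outside the mITT population.

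**What to change.** In SAP 8.1:

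1. Delete the clause on treated subjects, or limit it to efficacy (mITT) analyses. Deletion loses nothing for efficacy, since the mITT definition already requires a post-dose efficacy assessment.
2. State that every randomised and dosed subject counts in all Safety Population denominators, including the AE, exposure and protocol-deviation tables.
3. If the clause is kept for efficacy, replace *post-treatment follow-up* with *post-dose efficacy*, to match the mITT definition.
4. Note the change in SAP 2.2, because it departs from Protocol 9.3.1.

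The cost is a sentence or two in the SAP. No data collection, sample size or efficacy model changes.

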#### **8.1.1** Efficacy Assessment Windowing

For all efficacy analyses, windowing will be applied to ensure study day of assessment does not fall too far from scheduled assessment day. Assessments will be considered part of the scheduled visit window if they fall within  $\pm$ 3 days of the nominal study visit day. In the event of multiple assessments within the same visit window, the assessment closest to the nominal study day will be used. In the event of a tie, the

Form STAT401.V3 Page 9 of 23

Client/Project	Arrivo/Sirtsei 201
Version and Date	V01 August 26, 2022

earliest study day will be used. A visit must be completed within 2 days of last treatment dose to be included as a treatment period visit. Visits completed 3 or more days after last dose will be excluded from the treatment period analysis. Follow-up period windowing will be relative to date of last dose of study drug: assessments completed 3 to 10 days after the last dose of study drug will be windowed to the Week 5/1-Week Follow-up Visit.

Efficacy assessment listings will include both the reported and windowed visit labels. Any assessment completed outside of the windows for which that particular assessment was scheduled to be completed per the protocol will be labeled as "Out of Window".

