7. STUDY PROCEDURES AND ASSESSMENTS

7.1. Schedule of Events

The SOE for participants in the study is provided in [Table 2](#).

The actual dates of study drug administration and all study visits and assessments will be recorded in the subject's CRF. If a study visit or assessment occurs outside the specified time point and allowed time window (if applicable), then the reason for the deviation will be noted. Every attempt should be made to ensure that subsequent visits and assessments are performed on-time.

The Screening Period may be extended for extenuating circumstances, such as when additional time is needed for medication taper/washout or to repeat laboratory testing, with the approval of the medical monitor.

Study visits during the Treatment Period can be scheduled within a ± 3 day window relative to the Baseline Visit (i.e., the Week 1 Visit can be scheduled 7 ± 3 days relative to the completion of the Baseline Visit, the Week 2 Visit can be scheduled 14 ± 3 days relative to the completion of the Baseline Visit, the Week 3 Visit can be scheduled 21 ± 3 days relative to the completion of the Baseline Visit, etc.).

The Week 5 Visit can be scheduled 7 ± 3 days relative to the Week 4 / Premature Discontinuation Visit and the Week 6 Visit can be scheduled 14 ± 3 days relative to the Week 4 / Premature Discontinuation Visit.

Whenever ECGs, vital signs, and a blood draw for PK and/or safety labs are scheduled on a given day, the ECG and vital signs should be completed in the sequence of procedures either prior to the blood draw (preferred) or after the blood draw, such that the blood draw does not interfere with the ECG and vital sign recordings.

In addition to the study visits and assessments described in the SOE, unscheduled visits/assessments may be performed or repeated at the discretion of the Investigator if required to further evaluate laboratory parameters or the subject's clinical safety.

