**Table 8.1, Handling of Intercurrent Events** 

Estimand	Intercurrent Event	Rule / Rationale
Primary	Premature discontinuation /	Hypothetical "as own treatment" strategy. Clinical
	Permanent treatment	course is the same as other subjects in the same
	discontinuation	treatment group, who had not discontinued study
		treatment.
		Exclude observations that occur more than 3 days
		after the last dose of study drug for subjects who
		discontinue. The objective of the study is to
		evaluate the effect of SP-624 subjects who are
		provided drug to take on a standard schedule up to 4
		weeks. After 3 days, the drug should be cleared
		from all subjects, so the inclusion of any such data
		point is inconsistent with the goal of the estimand.
	Drug non-compliance / Missed	Treatment policy strategy.
	study medication	Some degree of non-compliance missed doses
		would be expected to occur in standard use.
	Protocol deviations not leading	Treatment policy strategy
	to study discontinuation	Overall, if not sufficient to lead to subject removal,
		the expectation is that they would not significantly
		impact subject results.
	Concomitant medications in	Treatment policy strategy
	violation of the protocol	This is expected to be a rare event in this clinical
		trial and treatment effect will be estimated
		irrespective of concomitant medication violations.

The hypothetical "as own treatment" strategy was selected for premature discontinuation or treatment discontinuation intercurrent events to evaluate the effect of treatment with respect to its pharmacologic efficacy. For the change from week 4 to week 5 follow-up secondary analysis, only subjects that were included in the week 4 primary analysis will be used. This should provide the most unbiased data for this

Form STAT401.V3 Page 12 of 23

Client/Project	Arrivo/Sirtsei 201
Version and Date	V01 August 26, 2022

phase 2 study to inform future studies. The treatment policy strategy will be used for all other defined intercurrent events.

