#### 8.3.6 Secondary Efficacy Endpoints

Seven secondary efficacy endpoints will be analyzed using the mITT populations. Where a model similar to the primary analysis is identified, the model may be reduced, if necessary, for convergence issues. These will be supported by descriptive summaries of results by group. These include:

- Change from Baseline to Weeks 1, 2, and 3 in MADRS total score for SP-624 vs. placebo. The outcome will be analyzed using the same methods as the primary outcome using estimate statement statements for each timepoint from the overall model.
- CGI-S is measured on a 7-point scale where 1 represents "normal" and 7 represents "most extremely ill". A summary of percentage of subjects with each score at Baseline and at Weeks 1, 2, 3, and 4 will be presented. The change from Baseline in CGI-S can take on interval values between -6 (improvement from 7 to 1) and 6 (worsening from 1 to 7). Treatment comparison of change from Baseline to Weeks 1, 2, 3, and 4 in CGI-S scores will be performed using an MMRM model similar to that of the primary efficacy variable.
- Change from Baseline to Week 5/1-Week Follow-up and change from Week 4 to Week 5 will be assessed for the MADRS and CGI-S. Treatment comparisons will be performed using an MMRM model similar to that of the primary efficacy variable.
- The HAM-D-17 is a 17-item scale whose total score can range from 0 to 52. Change from Baseline to Week 2 and Week 4 in the 17-item Hamilton Depression Rating Scale (HAM-D-17) total score will be assessed for treatment differences using an MMRM model similar to that of the primary efficacy variable.

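### The Week 5 efficacy window has no minimum study day, so the Baseline-to-Week 5 comparison can mix study times in a way that depends on dropout

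*SAP*

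**What the plan says.** SAP 8.1.1 separates on-treatment from follow-up efficacy scores by time since the last dose. For the treatment period, "A visit must be completed within 2 days of last treatment dose to be included as a treatment period visit", and "Visits completed 3 or more days after last dose will be excluded from the treatment period analysis". For follow-up, "Follow-up period windowing will be relative to date of last dose of study drug", and "assessments completed 3 to 10 days after the last dose of study drug will be windowed to the Week 5/1-Week Follow-up Visit". No minimum study day is attached. A score that fits no window scheduled for that assessment is labelled Out of Window.

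SAP 8.3.6 lists as a secondary endpoint "Change from Baseline to Week 5/1-Week Follow-up and change from Week 4 to Week 5" for MADRS and CGI-S, with treatment comparisons by an MMRM similar to the primary one. Both results are marked for the top-line package (Tables 14.2.4.1 and 14.2.6.1). For the Week 4-to-Week 5 change, the text under SAP Table 8.1 adds that "only subjects that were included in the week 4 primary analysis will be used". Nothing equivalent is said for Baseline to Week 5.

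The timing of the visit is given in three ways. Protocol 7.1 states that "The Week 5 Visit can be scheduled 7 ± 3 days relative to the Week 4 / Premature Discontinuation Visit". SAP Table 6.1 gives 7 ± 3 days after the last dose, which is days 4–10. SAP 8.1.1 gives days 3–10 after the last dose.

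**The concern.** SAP 8.1.1 opens by saying that windowing is there to keep the assessment day close to its scheduled day. For follow-up scores the rule does not do this. Time since Baseline plays no part, so a score from the second or third study week can carry the same Week 5 label as a completer's score from the fifth.

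At stake is the meaning of a secondary result. Change from Baseline in this indication depends on how long the subject has been in the study. If the share of early scores differs between arms, or if the arms separate over time, the Week 5 difference reflects dropout as well as treatment. The endpoint has also gained weight: Protocol 9.3.4.2 planned descriptive statistics for it, while the SAP tests it between arms. The last-dose anchor can also exclude a Week 5 visit that met the protocol's own timing.

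**Working it through.** The plan states no figure on this point to reproduce. The check enumerates the date windows.

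**Inputs**
- Treatment-visit windows, nominal day ± 3 (SAP 8.1.1): Week 1 Days 4–10, Week 2 Days 11–17, Week 3 Days 18–24, Week 4 Days 25–31.
- On-treatment limit: 2 days after the last dose (SAP 8.1.1).
- SAP Week 5 window: 3–10 days after the last dose (SAP 8.1.1).
- Protocol Week 5 visit: 4–10 days after the Week 4 / Premature Discontinuation visit (Protocol 7.1).
- Planned changes at Week 4: −12 for SP-624 and −9 for placebo (SAP 5). Typical dropout: 20–30% (SAP 8.3.5.5).

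**Step 1: study days that become Week 5.** For last dose on Day L the window is L+3 to L+10.

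| Last dose | Week 5 window | Treatment-visit windows overlapped |
|---|---|---|
| Day 7 | Days 10–17 | Week 1 (1 day), Week 2 (7 days) |
| Day 14 | Days 17–24 | Week 2 (1 day), Week 3 (7 days) |
| Day 21 | Days 24–31 | Week 3 (1 day), Week 4 (7 days) |
| Day 28 | Days 31–38 | Week 4 (1 day) |

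The whole window closes by the end of the Week 3 window when L + 10 ≤ 24, so L ≤ 14. Some part lies in a Week 1–3 window when L + 3 ≤ 24, so L ≤ 21. From Day 22 the overlap is with Week 4 only.

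**Step 2: would the protocol anchor alone cure this?** With the Premature Discontinuation visit 0–2 days after the last dose, the protocol's Week 5 visit falls on L+4 to L+12. For L = 14 that is Days 18–26. A completer whose Week 4 visit is on Days 25–31 has Week 5 on Days 29–41. The mixture remains, so the last-dose anchor is not its only source.

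**Step 3: protocol-timed Week 5 visits that fall out.** Take a subject whose Week 4 visit counts as on-treatment, so the lag from last dose to Week 4 visit is 0, 1 or 2 days. Days after last dose = lag + offset, with offset 4–10; the SAP limit is 10.
- Lag 0: days 4–10, 0 of 7 lost.
- Lag 1: days 5–11, 1 of 7 lost.
- Lag 2: days 6–12, 2 of 7 lost.

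That is 3 of 21 combinations (14%). Anchored to the Week 4 visit, 0 of 21 are lost.

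**Step 4: an illustration of size.** Assume linear improvement to −12 and −9 at Week 4, held to Week 5, with misplaced scores taken on average at Week 2 (−6 and −4.5). Let p (SP-624) and q (placebo) be the shares of Week 5 scores that are misplaced:

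difference = [−12(1−p) − 6p] − [−9(1−q) − 4.5q] = −3 + 6p − 4.5q

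- p = q = 0: −3.0
- p = q = 0.25: −3 + 1.5 − 1.125 = −2.625
- p = 0.30, q = 0.20: −3 + 1.8 − 0.9 = −2.1
- p = 0.20, q = 0.30: −3 + 1.2 − 1.35 = −3.15

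The last three set the misplaced share at the full expected dropout rate, so every dropout would have to return for a rating 3–10 days after the last dose. The unequal splits have no source in the documents, and these are raw means, not MMRM estimates.

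**The case against.** The best defence is that the visit is deliberately a one-week-off-drug assessment. The SAP names it Week 5/1-Week Follow-up, and for safety data SAP 8.1.2 justifies the same anchor as grouping subjects with similar exposure or follow-up. For a question about what happens after stopping, time since last dose is a reasonable anchor. It equalises time off drug, however, not time since Baseline, and change from Baseline to Week 5 depends on the latter.

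A reader might infer that routine Week 1–3 ratings will be relabelled Week 5 in bulk. The documents do not support that. Protocol 7.2.4 says not to rate at Weeks 1–4 or Premature Discontinuation after two or more consecutive missed doses, so most such scores should not exist. That rule does not name the follow-up visit, where MADRS and CGI-S are scheduled, so the affected scores would come mainly from early discontinuers' follow-up visits. These may be few: Protocol 5.4 asks such subjects to continue scheduled safety assessments, if possible. Off-drug ratings are still foreseen, because Protocol 9.3.4.1 takes Week 4 scores regardless of discontinuation and the SAP has rules for excluding them.

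A reader might also take 14% as the loss of Week 5 visits. It is a count of combinations with lags weighted equally and without a source. The Week 4 PK sample is due 2–10 hours post-dose (Protocol 7.2.6.1), which implies dosing on the visit day. At lag 0 nothing is lost, and visits timed by SAP Table 6.1 lose nothing either.

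The difference between 3–10 and 4–10 days is minor in itself: starting at day 3 leaves no gap after the on-treatment limit of day 2.

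**Conclusion.** The point holds as a defect in a stated rule for one secondary endpoint. Applied literally, SAP 8.1.1 admits off-drug scores from well before Week 5 into the Baseline-to-Week 5 comparison of MADRS and CGI-S, and no other SAP rule removes them. The cause is the absence of a minimum study day or Week 4 requirement, combined with last-dose anchoring in the SAP and Premature Discontinuation timing in the protocol.

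Neither effect can be sized from the documents. They do not say how many early discontinuers would return for a follow-up rating, how these would split by arm, or how the lag from last dose to Week 4 visit is distributed. A planned difference of 3.0 appearing as 2.6, 2.1 or 3.15 is an upper-end illustration as to the number of misplaced scores, not a prediction. Loss of protocol-timed Week 5 visits is possible only where the on-treatment Week 4 visit falls 1–2 days after the last dose.

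Two wider inferences fail. The primary Week 4 endpoint does not use the Week 5 label. The Week 4-to-Week 5 change is already restricted to subjects in the Week 4 analysis.

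**What to change.** In SAP 8.1.1 and 8.3.6:

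- Let a score count as Week 5 in the Baseline-to-Week 5 MMRM only for subjects with a valid on-treatment Week 4 record, which is the restriction already applied to the Week 4-to-Week 5 change.
- For these subjects, use the protocol timing of 7 ± 3 days after the Week 4 visit.
- Keep early discontinuers' on-treatment Week 1–4 scores in that model, with Week 5 treated as missing. This matches the hypothetical strategy in SAP Table 8.1 and avoids selecting the model's population on completion. State that the Week 5 model contains Weeks 1–4 as well.
- Summarise early discontinuers' off-drug scores separately, labelled as one week after discontinuation.
- Reconcile the 3–10 day rule in 8.1.1 with the 7 ± 3 days in Table 6.1. At the same time, reconcile the on-treatment cut-off: 8.1.1 excludes visits 3 or more days after the last dose, while Table 8.1 excludes those more than 3 days after it, so day 3 is handled in two ways.

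The cost is SAP wording and a small programming change. The statistical price is fewer observed Week 5 scores and reliance on missing-at-random for early discontinuers.
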